14.3.18 Annualized Relapse Rate (ARR) between Baseline and 12/24 months

The unadjusted ARR will be calculated for the Treatment Period, Course 1 Treatment Period and Course 2 Treatment Period.

The unadjusted ARR for a subject i is defined as the number of relapses per year:

- ARR for subject i = number of relapses during the Period / person-years of subject i ,
- Person-years for subject i = Period (in days) / 365.25.

The unadjusted population ARR is the mean of all subject's ARR. The unadjusted ARR will be calculated for all relapses, as well as the qualifying relapses (ARR_{qual}), as reported in the eCRF.

Relapses will be counted for the defined time Period, if the date of onset of the relapse is within the defined time Period. Incomplete or missing onset dates will be imputed as specified in Section 9.

The number of subjects with (qualifying) relapses, the number of (qualifying) relapses, person-years and the unadjusted population ARR will be presented for the Treatment Period, Course 1 Treatment Period and Course 2 Treatment Period. Also, the number of subjects with relapses and number of relapses which were treated with steroids or leading to hospitalization will be presented separately. For the Interim Analysis the different relapse counts up to the month 6 Visit will be presented without the ARR.

In addition, the relapse rate will be analyzed using a Poisson regression model with count of relapses as dependent variable and with fixed effects for age (in years) and EDSS at Baseline (≤ 3 , > 3). The log of the duration of the treatment Period (precision in days) will be the offset variable in the model.

Analysis (Analysis Set)	Derivation	Statistical Analysis Methods	Missing data handling
Tertiary endpoint: Annualized relapsed rate (ARR) between Baseline and Month 12 and Month 24			
Tertiary (FAS)	ARR during the Treatment Period	Poisson regression for number of relapses. Adjusting factors: 
 • Age (in years), • EDSS at Baseline ($\leq 3 / > 3$). • Log of the duration of the Treatment Period (in days) as offset. Estimated mean ARR and corresponding Standard Errors (SE) will be presented, including 2-sided p-values and 95% CIs. In addition, the unadjusted ARR will be presented descriptively.	The analysis will consider the different observation Periods of early withdrawals by including the treatment Period as offset in the analysis. This strategy is assuming MAR.
Tertiary (FAS)	ARR during the Course 1 Treatment Period		
Tertiary (FAS)	ARR during the Course 2 Treatment Period		
Tertiary (FAS)	ARR _{qual} during the Treatment Period		
Tertiary (FAS)	ARR _{qual} during the Course 1 Treatment Period		
Tertiary (FAS)	ARR _{qual} during the Course 2 Treatment Period		
Tertiary (FAS)	ARR leading to hospitalization during the Treatment Period		
Tertiary (FAS)	ARR requiring steroid treatment during the Treatment Period		

For the 6-month IA, all relapses during first 6 months will be listed together with relevant MRI results (T1, T2 and CUA lesion counts) by subject.

CCI

CCI

CCI

CCI

CCI

CCI

CCI

CCI

CCI

CCI

CCI

CCI

CCI

CCI

CCI

CCI

CCI

CCI

CCI

15 Safety Analyses

The subsections in this section include specifications for summarizing safety endpoints that are common across clinical studies such as adverse events, laboratory tests and vital signs.

Safety analyses will be done on the SAF. Unless otherwise specified, the safety analysis will be done for interim and final analysis.

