MRI scans including lesion count, lesion volume, brain atrophy and MTR will be performed at screening, Baseline, and the end of Months 1, 2, 3, 6, 12, 15, 18, and 24. There will be a gap of at least 4 weeks between MRIs performed at screening and Baseline. Neurological examinations including EDSS/KFS, 9HPT, and T25FW will be performed at screening, Baseline, and the end of Months 6, 12, 18 and 24. SDMT will be performed at Baseline, and the end of Months 6, 12, 18 and 24. Blood specimens for immune cell subtypes count will be collected at Baseline, and the end of Months 3, 6, 12, 15, 18, 24. Physical examination including recording of vital signs will be performed at screening, Baseline, and Months 6, 12, 18 and 24. Safety laboratory tests including lymphocyte count, Hepatitis B and C, active and latent TB, HIV and urine/serum pregnancy test will be carried out at screening and before initiating second treatment course at Month 12; lymphocyte count will also be checked at 2 and 6 months after each treatment. If the absolute lymphocyte count at screening is done more than 4 weeks prior to Baseline, it should be repeated within 4 weeks of Baseline.

Subjects who discontinue Mavenclad[®] at any time during the trial will continue to participate in the scheduled visit for assessments. In the event of early discontinuation from the trial, the subject should return for the Early Termination visit for final assessment.

Following a relapse, subject may receive treatment with either acute short-term systemic corticosteroids or ACTH or plasma exchange at the discretion of the Investigator, following local good medical practice and international guidelines. A subject receiving any rescue medication with any other DMD will be followed-up by the investigator as standard of routine practise and will not participate further in any trial assessments; the subject should however complete the early termination visit for final assessment.

If a subject prematurely withdraws from the trial at any time, he/she will undergo all tests requested at the Early Termination visit as soon as possible.

Visit schedules for efficacy and safety assessments are detailed in [Appendix 1: Schedule of Assessments](#).

CCI [REDACTED]

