5.5 Criteria for Subject Withdrawal

5.5.1 Withdrawal from Trial Therapy

Withdrawal may be considered in the following cases:

- Any subject that does not fulfil the above-mentioned criteria (Section 5.4) for the first and/or the second course of treatment
- Occurrence of latent infection such as herpes zoster, hepatitis or tuberculosis reactivation. In this case adequate anti infection treatment should be initiated and withdrawal from or delay of second course of Mavenclad® should be considered

If recovery from lymphopenia and/or infectious disease takes more than 6 months, the subject should not receive the second treatment course of Mavenclad®.

Withdrawal is mandatory in the following cases:

- Withdrawal of consent
- Protocol violation, including non-compliance that, in the opinion of the Investigator or Sponsor necessitates the subject being removed. The decision to withdraw the subject should be taken in consultation with the Medical Monitor
- Lost to follow-up
- Pregnancy
- Live or live attenuated vaccine at any time during the trial duration (except anti-herpes prophylaxis following a drop in lymphocyte count below 200 cells/mm³)
- Initiation of treatment with an experimental drug
- Initiation of treatment with another disease modifying therapy for multiple sclerosis
- Occurrence of active malignancies
- Presence of signs of PML detected by MRI, clinical and/or biomarker evaluations
- Occurrence of an exclusion criterion that is clinically relevant and affects the subject's safety, if discontinuation is considered necessary by the Investigator and/or Sponsor
- Lymphocyte count less than 800 cells/mm³ for more than 6 months before initiation of second treatment course
- HIV infection, active tuberculosis and active hepatitis before initiation of second treatment course
- Any events that unacceptably endanger the safety of the subject

If a subject is lost to follow-up, every possible effort must be made by trial center personnel to contact the subject and determine the reason for discontinuation. The measures taken to follow-up must be documented. If a subject discontinues before completion of trial procedures, the reason for discontinuation must be documented in the case report form (CRF) and source documents.

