Subjects who discontinue cladribine tablets at any time during the trial will continue to participate in the scheduled visits for assessments until his/her planned trial completion. In the event of early discontinuation from the trial, the subject should return for the Early Termination visit for final assessment.

For subjects who experience a relapse and initiated on another DMD (as per investigator's discretion), the subject will not participate further in any trial assessments and be followed-up by the investigator as standard of routine practice. The subject should however complete the early termination visit for final assessment.

Withdrawn subjects will not be replaced.

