6.5.1.4 Relapse Management

In case of neurological events related to multiple sclerosis, with relapse criteria met (Section 7.3.3), treatment with either acute short-term systemic corticosteroids or ACTH or plasma exchange can be administered at the discretion of the Investigator, following local good medical practice and international guidelines. The Investigator must complete the evaluation prior to treatment with steroids or other therapeutic intervention(s) that may alter the subject's neurological state.

Upon Investigator's judgement, any relapse that is considered severe should be treated and followed up as per standard of routine practice. In case of subject receiving treatment with any

other DMDs, the subject will be discontinued from the trial and will not undergo any trial related scheduled assessments; the subject should however complete the early termination visit for final assessment.

The initiation of second treatment course with Mavenclad[®] following acute management of relapse will be at investigator discretion.

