- Period 100.1 (p_{100.1}) is defined as the Period between Baseline and Month 1 MRI scans,

- Period 100.2 (p_{100.2}) is defined as the Period between Month 1 and Month 2 MRI scans,
- Period 100.3 (p_{100.3}) is defined as the Period between Month 2 and Month 3 MRI scans,
- Period 100.6 (p_{100.6}) is defined as the Period between Month 3 and Month 6 MRI scans,
- Period 100.12 (p_{100.12}) is defined as the Period between Month 6 and Month 12 MRI scans,
- Period 100.15 (p_{100.15}) is defined as the Period between Month 12 and Month 15 MRI scans,
- Period 100.18 (p_{100.18}) is defined as the Period between Month 15 and Month 18 MRI scans,
- Period 100.24 (p_{100.24}) is defined as the Period between Month 18 and Month 24 MRI scans.

Note: Period start and end dates are defined by the MRI dates as provided by central reading.

Definition of change from Baseline

Change from Baseline = Visit value – Baseline value.

Percentage Change from Baseline = $100 \times (\text{Visit value} - \text{Baseline value}) / \text{Baseline value}$.

The Percentage Change from Baseline will be set to missing for subjects with a zero at Baseline.

Definition of Visit dates

The Visit start date is the date of the first assessment which belongs to the corresponding Visit.

The Visit end date is the date of the last assessment which belongs to the corresponding Visit.

Definition of duration

Duration will be calculated by the difference of start and stop date + 1, in days (unless specified otherwise).

Treatment Period

The treatment Period begins with the start of study medication on Study Day 1 and continues through to the completion of the treatment Period at the Month 24 Visit (see CSP, Section 7.1.2). Start of study medication is the date of first intake of study medication. Start of study medication in Year 2 is the date of first intake of study medication at or after the Month 12 Visit.

Treatment Period:

- Start = Start of study medication,
- End = Visit end date of Month 24 Visit, or Early Termination (ET) Visit, in case of early discontinuation, or the study discontinuation date, if the ET Visit was not performed.

Course 1 Treatment Period:

- Start = Start of study medication,

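### The descriptive unadjusted population ARR is a plain mean of subject-level rates, so it runs high and is less precise when relapsers leave early to start another DMD

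*SAP*

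**What the plan says.** SAP 14.3.18 sets a subject's ARR as that subject's relapses in the period divided by that subject's person-years, where person-years are the period in days over 365.25. It continues: "The unadjusted population ARR is the mean of all" of these subject-level values. This is done for the Treatment Period and for the Course 1 and Course 2 Treatment Periods, for all relapses and for qualifying relapses. On display, "The number of subjects with (qualifying) relapses, the number of (qualifying) relapses, person-years and the unadjusted population ARR will be presented" for the three periods, and the analysis table adds: "In addition, the unadjusted ARR will be presented descriptively".

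The length of the period comes from SAP Section 9. The Treatment Period ends at the Month 24 visit, or at the Early Termination visit "in case of early discontinuation, or the study discontinuation date, if the ET Visit was not performed".

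The protocol decides who has a short period:

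- Section 5.2: "A subject receiving any rescue medication with any other DMD" takes no further part in trial assessments apart from the early termination visit.
- Section 5.5.1, on a subject who relapses and starts another DMD: "the subject will not participate further in any trial assessments".
- Section 6.5.1.4, on a subject given "other DMDs, the subject will be discontinued from the trial and will not undergo any trial related scheduled assessments".
- Section 5.5.1 also states that withdrawn subjects are not replaced.

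The model-based ARR in SAP 14.3.18 is a Poisson regression with log duration as offset.

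**The concern.** A plain mean of individual rates gives a record of 60 days the same weight as a record of two years. That would cost only precision if short follow-up had nothing to do with relapse. Here the protocol ties the two together: a subject who switches DMD because of a relapse has at least one relapse in the numerator and a truncated denominator. The subject's rate is then very large and pulls the mean up.

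The figure will stand beside the Poisson ARR for the same period and may be visibly higher only because of how it was averaged. A reader could take that gap for a covariate effect or a finding. SAP Section 4 allows the planned results to go into the study report, regulatory submissions and manuscripts, so the number may travel without its definition.

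**Working it through.** **Inputs from the documents.** N is about 265 (protocol synopsis) and follow-up is 2 years. The readable text gives no relapse rate, share of relapsers who switch, or time from relapse to exit. There is therefore no planned figure to reproduce, and those three inputs are assumed over a range.

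**The two estimators.** With relapses n_i and person-years T_i:

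- SAP: (1/N) × Σ(n_i / T_i), where each subject has weight 1/N.
- Pooled: Σn_i / ΣT_i, where each subject's rate has weight T_i / ΣT. A Poisson model with a log-time offset and no covariates returns this value.

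If relapse can end follow-up, n_i and 1/T_i are positively related and the mean of n_i/T_i exceeds the true rate. If all subjects share one rate, the pooled ratio stays on target. If rates differ, high-rate subjects leave sooner and the pooled ratio runs somewhat low.

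**One leaver, by direct arithmetic.** Take 264 subjects followed for 730 days at a mean rate of 0.300, plus one subject with one relapse. The 264 contribute 264 × 730/365.25 = 527.64 person-years and 0.300 × 527.64 = 158.29 relapses.

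- Exit at day 60: own rate 365.25/60 = 6.09 per year. SAP mean (264 × 0.300 + 6.09)/265 = 0.322, or +7.3%. Pooled 159.29/(527.64 + 0.16) = 0.302, or +0.6%.
- Exit at day 180: SAP mean +2.2%, pooled +0.5%.
- Exit at day 365: SAP mean +0.9%, pooled +0.4%.

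**Simulation.** N = 265, 730 days, true ARR 0.30, subject rates gamma-distributed with shape 1, 4% per year unrelated dropout, 1,500 trials per setting. Bias of the SAP mean against the true rate (Monte Carlo standard error 0.2 to 0.4 percentage points):

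| Share of relapses leading to a switch (subjects) | Exit 7–60 days after relapse | Exit 60–180 days after relapse |
|---|---|---|
| 0% | none | none |
| 1% (1–2) | +2.7% | +0.4% |
| 2% (about 3) | +4.6% | +1.7% |
| 5% (6–7) | +10.9% | +4.4% |
| 10% (12–14) | +20.9% | +9.3% |

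Across true ARR 0.15 and 0.30, with and without between-subject variation, the ranges are +11 to +12% / +4 to +5% at 5% switching and +21 to +22% / +9 to +10% at 10%. The pooled rate stayed within −2.3% to +0.5% of the truth over this grid.

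The SD of the SAP mean relative to the SD of the pooled rate was 1.05 with no switching, 1.12 to 1.21 at 1–2%, 1.50 / 1.17 at 5% and 1.73 / 1.27 at 10%.

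**By course**, approximating Course 1 as year 1 and Course 2 as year 2 (ARR 0.30, shape 1):

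- Course 1: +7.9% / +2.1% at 5% switching and +15.5% / +4.6% at 10%.
- Course 2: +6.7% / +0.9% and +12.8% / +2.4%.

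**Heavier switching.** A second grid used 720 days, true ARR 0.1 to 0.4, 5% unrelated dropout over two years and 600 trials per setting. The SAP mean was biased by +26 to +29% when 25% of relapses led to exit at 90 days, +47 to +54% when 25% led to exit at 30 days, and +87 to +105% when 50% led to exit at 30 days. The pooled rate was within about 1% when subjects shared one rate, and between 0 and −14% off when rates varied strongly.

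**The case against.** The strongest case is that this is a presentational preference. The protocol's ARR analysis (Section 8.5.3) is a Poisson model with an offset for time under observation. The SAP keeps it and says that the offset is how early withdrawals are handled. The mean of rates is labelled unadjusted and descriptive, no test uses it, and any reader can form the pooled ratio from the relapse counts and person-years in the same table. All of that stands, and it is why the point is minor. It does not make the less stable number the right one to print as the population ARR. The SAP itself sums exposure across subjects for its exposure-adjusted adverse event rates (Section 15.1.1).

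Second, the bias depends on inputs the documents do not give. Relapses may be treated acutely without leaving the trial, and subjects who only stop study drug continue their visits. With 1–2% switching and slow exit the excess is only 0.4 to 1.7%, and the day-60 example is the steepest of the three shown. This stands: the algebra is certain, the size in this trial is not.

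Third, the pooled rate is not free of bias. It runs low when high-rate subjects leave, which favours the drug, by up to 14% under the heaviest switching examined. This also stands, but in those settings the mean of rates was far further off in the other direction.

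Finally, the by-course simulation does not follow SAP Section 9 exactly. There, Course 1 ends the day before Course 2 starts, or 457 days after the first dose if Course 2 is never given, and efficacy data after Course 1 count as missing when Course 2 is delayed. The by-course percentages are illustrative only.

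**Conclusion.** The concern holds and is minor. As defined, the unadjusted population ARR overstates the relapse rate whenever relapse leads to a switch and early exit, and it is less precise than the pooled rate. If 5 to 10% of relapses lead to a switch, the excess is roughly 4 to 21%, depending on how soon subjects leave, and the SD is about 1.2 to 1.7 times the pooled SD. With no switching there is no bias and almost no loss of precision; with much heavier switching the excess could pass 50%. These sizes rest on the assumed relapse rate, switch share and exit lag. No test or model-based estimate is affected.

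A wording point goes with it. The SAP table names the Treatment Period as the Poisson offset, while the course rows need their own period. The intent is clear from protocol Section 8.5.3, but it should be stated.

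**What to change.** In SAP 14.3.18, replace the sentence defining the unadjusted population ARR so that, for each period, it is total relapses divided by total person-years. If the mean of individual rates is kept, show it only as a labelled supplement. If a confidence interval is added, allow for overdispersion. As a tidy-up, state that the offset in each Poisson model is the log of that row's own observed period.

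The cost is one sentence, plus a clause for the offset. Relapse counts and person-years are already tabulated, so no new data or derivation is needed. The change does not cure informative exit: with ARR 0.30 and gamma shape 1 the pooled rate still runs 1.1 to 1.4% low at 5% switching and 2.0 to 2.3% low at 10%. A footnote giving the number of subjects who left after starting another DMD would let readers judge this.

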8.5.3 Analysis of Secondary and Tertiary Endpoints

Analysis comparing continuous secondary and tertiary endpoints measured repeatedly at specific time points to baseline will be undertaken using similar techniques to those outlined for the primary analysis while taking the within-subject correlation into account where appropriate. Linear regression modelling assumes that outcomes are normally distributed. Appropriate transformations (such as square root or log transform) may be used to achieve normality. Alternatively, nonparametric methods may be applied.

Annualized relapse rate will be evaluated using a Poisson regression model with count of relapses as dependent variable and with age and EDSS as covariates. The log of time under

observation (in days) will be the offset variable in the model. Categorical endpoints will be analyzed by logistic regression.

Safety endpoints will be summarized descriptively, providing detail of the frequency, type, severity and outcome of the events.

Other outcomes will be summarized descriptively.

CCI

CCI

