- End = Start of study medication at or after the Month 12 Visit - 1 day, or if the subject did not receive Treatment Course 2: Start of study medication of Treatment Course 1 + 457 days (which is obtained by 360 (12 months) + 90 (3 months) + 7 (Visit window)) or date of discontinuation, if earlier.

Course 2 Treatment Period:

- Start = Start of study medication at or after the Month 12 Visit,
- End = End of Treatment Period.

Definition of Delayed Treatment Course 2

The Treatment Course 2 will be defined as delayed, if the start of study medication is delayed by more than 3 months (= 90 days) or did not start at all i.e.:

- Start of Study medication of Treatment Course 2 > Start of Study Medication of Treatment Course 1 + 457 days (which is obtained by 360 (12 months) + 90 (3 months) + 7 (Visit window)), or
- Treatment Course 2 never started (i.e., no study medication taken at or after the Month 12 Visit).

Data handling in case of a Delayed Treatment Course 2

For subjects with a Delayed Treatment Course 2, only data observed during the Course 1 Treatment Period will be analyzed in all efficacy analyses. Efficacy data after the Course 1 Treatment Period will be counted as missing in the statistical analyses and marked in the listings. In all efficacy analyses defined by Period, the subject will be classified as if the subject discontinued at the end of the Course 1 Treatment Period. For subjects without a delay the whole Treatment Period will be analyzed.

For all other analyses (except efficacy) the data is not limited to the Course 1 Treatment Period for subjects with a Delayed Treatment Course 2.

Definition of start of COVID-19-Pandemic

The start of COVID-19 pandemic will be defined by country as the earliest date of either the date of the first death from COVID-19 occurred in each country according to the published data by European Centre for Disease Prevention and Control on 26th June 2020 (<https://www.ecdc.europa.eu/en/publications-data/download-todays-datageographic-distribution-covid-19-cases-worldwide>) or 11th March 2020 (when the WHO declared COVID-19 pandemic).

Visit timing with respect to COVID-19 pandemic

A Visit is defined to be performed after the start of COVID-19 pandemic if the Visit end date is greater than the start of COVID-19 pandemic date.

Conversion factors

The following conversion factors will be used to convert days into months or years for all observations except Visit related dates:

- 1 month = 30.4375 days,

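### The Poisson model for relapse rates makes no allowance for overdispersion, and its one stated offset does not name the course-specific periods

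*SAP*

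**What the plan says.** **Model.** Protocol 8.5.3: "Annualized relapse rate will be evaluated using a Poisson regression model", with age and EDSS as covariates. SAP 14.3.18 repeats this: "the relapse rate will be analyzed using a Poisson regression model with count of relapses as dependent variable", with fixed effects for age in years and baseline EDSS (≤3, >3). Neither section names a scale parameter, robust standard errors or a negative binomial alternative for relapses. Estimated rates with standard errors, two-sided p-values and 95% confidence intervals are planned.

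**Offset.** The SAP narrative says: "The log of the duration of the treatment Period (precision in days) will be the offset variable in the model". The table's methods cell says: "Log of the duration of the Treatment Period (in days) as offset". The table has eight rows. Four of them are course-specific, such as "ARR during the Course 1 Treatment Period", and state no offset of their own.

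**Periods.** SAP Section 9 defines three. The Treatment Period runs from first dose to "End = Visit end date of Month 24 Visit, or Early Termination (ET) Visit" (or the discontinuation date if there was no ET visit). The Course 1 Treatment Period ends at "Start of study medication at or after the Month 12 Visit - 1 day". If Course 2 is not given, it ends 457 days after the start ("360 (12 months) + 90 (3 months) + 7 (Visit window") or at discontinuation, if earlier. The Course 2 Treatment Period takes up the remainder.

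**The concern.** A Poisson model fixes the variance at the mean, given the covariates. The documents themselves point to further sources of variation:

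- Eligibility admits both subjects with one relapse in the prior year while on a DMD and subjects with two or more.
- SAP 8.2 makes high relapse activity and prior DMD use subgroups, but neither enters the relapse model.
- Protocol 8.5.1 expects correlation within sites, but the relapse model has no center term.

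If such variation remains, the rate itself is still estimated soundly, but its standard error is too small and the interval covers less often than stated.

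The offset is a separate matter. Treatment Period is a defined term of about two years. A programmer who applies it word for word to a Course 1 row would divide about one year of relapses by about two years of follow-up.

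**Working it through.** The documents state no relapse rate, dispersion or ARR-based power, so there is no planned figure to reproduce.

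**Overdispersion**

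Assumed, not in the documents: rates of 0.2 and 0.4 relapses per year; dispersion k from 0 to 2 with variance mu + k·mu². From the SAP: a 360-day visit year, so 24 months = 720 days = 720/365.25 = 1.97 years, and a two-sided 95% level.

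- True SE / Poisson SE = √(1 + k·mu).
- Actual coverage = 2Φ(1.96/√(1 + k·mu)) − 1.
- Example: rate 0.2 gives mu = 0.2 × 1.97 = 0.394. At k = 1, √1.394 = 1.18 and coverage is 90.3%.

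| Rate per year, period | k = 0 | k = 0.5 | k = 1 | k = 2 |
|---|---|---|---|---|
| 0.2, 24 months: SE ratio | 1.00 | 1.09 | 1.18 | 1.34 |
| 0.2, 24 months: coverage | 95% | 92.7% | 90.3% | 85.7% |
| 0.2, 24 months: simulated | 96.3% | 92.8% | 91.0% | 86.8% |
| 0.4, 24 months: SE ratio | 1.00 | 1.18 | 1.34 | 1.61 |
| 0.4, 24 months: coverage | 95% | 90.3% | 85.7% | 77.8% |
| 0.4, 24 months: simulated | 95.1% | 90.1% | 87.1% | 77.7% |
| 0.2, 12 months: coverage | 95% | 93.9% | 92.7% | 90.3% |
| 0.4, 12 months: coverage | 95% | 92.7% | 90.3% | 85.7% |

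The simulations used 1000 trials per cell, 265 subjects, 10% drop-out (assumed) and a Poisson model with age and EDSS. The rows for relapses that led to hospitalization or needed steroids have a smaller mu, so on the same formula the effect is smaller.

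**Offset applied literally**

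Bias factor for Course 1 = Course 1 days / Treatment Period days.

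- Completer with Course 2 on time: 360/720 = 0.50.
- Course 2 started at the 457-day limit, Month 24 falling 360 days later: 457/817 = 0.56.
- Course 2 never started, followed to Month 24: 457/720 = 0.63.
- Drop-out in year 1: 1.00.

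Pooled over 265 subjects, with assumed drop-out of 0% to 20% (at day 180) and 0% to 10% without Course 2, the factor is 0.50 to 0.55. The upper end is (185.5×360 + 26.5×457 + 53×180)/(212×720 + 53×180) = 88,430.5/162,180 = 0.545. In simulation with 10% drop-out it was 0.514: a true Course 1 rate of 0.20 was estimated as 0.101 with the literal offset and 0.197 with Course 1 days.

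The Course 2 rate is also roughly halved: 360/720 = 0.50 if on time, 360/817 = 0.44 for a start at the limit.

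**Overall ARR when Course 2 is delayed or absent**

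SAP Section 9 treats efficacy data after the Course 1 Treatment Period as missing for these subjects. If their offset still ran to Month 24, uncounted time would enter even the overall rate: for a subject never given Course 2, only 457 of 720 days (0.63) would be observed.

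**The case against.** On the intervals, the case against is that nothing in the documents shows relapse counts to be overdispersed. At k = 0 coverage is nominal, and low rates or short periods leave little to correct. Protocol 8.5.1 commits to examining the assumptions of the regression models. The negative binomial models for lesion counts do not prove that relapses need one.

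Most of this stands. The loss of coverage is conditional, and a check is planned. But that clause only allows alternatives to be considered in addition. It names none for relapses, and the Poisson interval would still be reported.

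On the offset, the stated wording is right for the row beside it, and the blank cells below may be one merged cell. Other text shows the intent:

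- The unadjusted ARR in the same section divides by person-years of the period concerned.
- The narrative writes treatment without a capital.
- The missing-data cell speaks of differing observation periods.
- Protocol 8.5.3 uses observation time as offset, and SAP Section 7 lists no change to it.
- Section 9 treats subjects with a delayed or absent Course 2 as discontinued at the end of Course 1 in efficacy analyses defined by period.
- Unadjusted rates are reported alongside, so a twofold gap would be noticed.

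This also stands. The wording is inconsistent, but the intended offset can be recovered.

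**Conclusion.** Two limited points hold.

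First, the plan fixes a plain Poisson variance for relapses. If counts vary beyond age and EDSS category, the 95% intervals are too narrow. At an assumed 0.2 to 0.4 relapses per year over 24 months, coverage is about 93% to 90% at k = 0.5 and 90% to 86% at k = 1. The loss is smaller for one-year periods and relapse subsets, and there is none at k = 0.

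Second, the table leaves the offset of the course-specific rows unstated. The literal reading would give about 0.50 to 0.55 of the true Course 1 rate and about half the Course 2 rate.

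A reader might infer more, and the documents do not support it:

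- **That the intervals are too narrow as a matter of fact.** No dispersion figure is given.
- **That the reported Course 1 rate will be halved.** That needs a reading that conflicts with the unadjusted formula and the protocol.
- **That a main result of the trial is at risk.** ARR is tertiary, all non-primary analyses are exploratory, and the primary analysis does not use this model.

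**What to change.** In SAP 14.3.18, for all eight ARR rows:

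1. Use Poisson regression with Pearson-scaled or robust (sandwich) standard errors, or negative binomial regression, and name the choice in advance.
2. State the offset as the log of the observed duration of the same period in which the relapses are counted: Treatment Period, Course 1 or Course 2.
3. State that, for subjects with a delayed or absent Course 2, the observed duration ends at the end of the Course 1 Treatment Period, in line with Section 9.

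The cost is a few words in the SAP and a change to the model statement. Intervals become somewhat wider if overdispersion is present and hardly change if it is not. No additional data are needed.
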